10.21.4 AE Duration

The AE duration (expressed in days) will be defined as:

- AE stop date – AE start date + 1 day.

The duration will not be derived in case of partial or missing start or stop date.

Based on the above value the AE duration will also be categorized as follows:

- 1-7 days,
- 8 to 14 days,
- 15 to 28 days,
- 28 to 42 days,
- 43 to 61 days,
- > 61 days,
- Ongoing,
- Indeterminate.

If AE stop date is missing and the outcome of the AE is “Not recovered, Not resolved”, the AE will be categorized as “Ongoing”.

If the AE start date is partial or missing and the AE is not considered as “Ongoing”, the AE will be classified as “Indeterminate”.

If AE duration is less than 1 day, the AE will be counted in the 1-7 days category.

10.22 Laboratory data

Strip-sign handling

In cases a hematology or chemistry value is recorded as ‘>x’ or ‘’, the value will be imputed as “x” to perform summary statistics but the strip sign will be presented in individual data listings.

10.23 Columbia Suicide Severity Rating Scale (C-SSRS)

The C-SSRS scale is composed of 11 items answered Yes or No. Ten of them are ordered in categories as described below to determine the studied endpoints.

5 subtypes of suicidal ideation:

- Category 1 – Wish to be Dead,
- Category 2 – Non-specific Active Suicidal Thoughts,
- Category 3 – Active Suicidal Ideation with Any Methods (Not Plan) without Intent to Act,
- Category 4 – Active Suicidal Ideation with Some Intent to Act, without Specific Plan,
- Category 5 – Active Suicidal Ideation with Specific Plan and Intent.

5 subtypes of suicidal behavior:

- Category 6 – Preparatory Acts or Behavior,
- Category 7 – Aborted Attempt,
- Category 8 – Interrupted Attempt,
- Category 9 – Actual Attempt (non-fatal),
- Category 10 – Completed Suicide.

Last item:

- Self-injurious behavior without suicidal intent.

The C-SSRS also includes a suicidal ideation intensity rating from 1 (least severe) to 5 (most severe).

The following composite endpoints will be assessed based on the categories described above:

- Suicidal ideation (Yes/No): is Yes if one of the categories from 1 to 5 is answered Yes,
- Suicidal behavior (Yes/No): is Yes if one of the categories from 6 to 10 is answered Yes,
- Suicidal ideation or behavior (Yes/ No): is Yes if one of the categories from 1 to 10 is answered Yes,
- Self-injurious behavior without suicidal intent (Yes /No): is Yes if this question is answered Yes.

The following scores will be derived as follows:

- Suicidal ideation score is rating from 1 to 5 the most severe suicidal ideation category answered Yes and is assigned to 0 if categories 1 to 5 are answered No,

- Suicidal ideation intensity rating score (0 to 25) will be defined as the sum of the 5 features described below (ranging from 0 to 5, 0 being the least severe and 5 being the most severe) rated with respect to the most severe type of ideation category,
 - Frequency,
 - Duration,
 - Controllability,
 - Deterrents,
 - Reason for ideation.

Comparative endpoints will also be defined as described below:

Treatment emergent outcomes will include any events that first emerge or worsen, whereas emergent outcomes will refer to outcomes that first emerge.

- Treatment-emergent suicidal ideation compared to recent history (not using C-SSRS taken during screening):
 - Increase from baseline in suicidal ideation score,
 - Increase from last on-treatment visit to follow-up (FU) visit,
- Treatment-emergent serious suicidal ideation compared to recent history (not using C-SSRS taken during screening):
 - Increase in suicidal ideation score from a baseline (0-3) to (4-5),
 - Increase in suicidal ideation score from last on-treatment visit (0-3) to FU visit (4-5),
- Emergence of a serious suicidal ideation compared to recent history (not using C-SSRS taken during screening):
 - Increase in suicidal ideation score from baseline (0) to (4-5),
 - Increase in suicidal ideation score from last on-treatment visit (0) to FU visit (4-5),
- Emergence of suicidal behavior compared to all prior (using C-SSRS taken at and post screening assessments):
 - Occurrence of suicidal behavior (categories 6-10) post baseline with no screening or baseline suicidal behavior,

No imputation should be done with regards to missing data.

11.0 Interim Analyses

No interim analysis will be conducted.

However, a blinded assessment of the estimate of the variability of the treatment difference will be conducted during the study and the sample size recalculated using this blinded estimate. The study will still be ongoing at time of these blinded analyses and the decision whether or not to increase the sample size will be based on the Sponsor judgment.

This blinded review of the data will take place once, using the first 50% of the patients, from FAS, having completed both treatment periods, and for whom all MAS assessment data are cleaned (no open queries), coded and reconciled.

11.1 Blinded Sample Size Reassessment

The sample size estimate as described in [Section 8.2](#) was assuming mean treatment difference of -0.30 and a standard deviation of paired difference of 0.71.

Let d_i denote the difference between Period 2 and Period 1 for Patient i ($i = 1$ to n) when n is the number of patients, at the interim analysis, having completed Period 1 and Period 2 on-treatment and for whom LLMT-6 score (as described in [Section 10.16](#)) can be derived for both treatment periods.

Let \bar{d} is the overall mean of all d_i

When the n patients complete the assessment on the primary endpoint, the variability is estimated by pooling all the patients as follows

$$\hat{\sigma}_{diff}^2 = \frac{1}{(n-1)} \sum_i^n (d_i - \bar{d})^2$$

The re-calculated sample size is given by

$$\hat{N} = \frac{(t_{1-\alpha} + t_{1-\beta})^2}{\delta^2} \hat{\sigma}_{diff}^2$$

That is,

$$\hat{N} = \frac{(t_{1-\alpha} + t_{1-\beta})^2}{\delta^2} \frac{1}{(n-1)} \sum_i^n (d_i - \bar{d})^2$$

where δ is the target treatment effect size. This re-calculated sample size will be provided to the sponsor to aid decision-making; however the sponsor has the final decision as to whether to increase the sample size and to what number.

11.2 Other Analyses

Baseline efficacy endpoints will be summarised and no other additional analyses are planned during the blinded sample size reassessment.

12.0 Statistical Methods

All analyses will use SAS® version 9.4 or higher. However, pharmacokinetic analyses may be performed using a dedicated software as mentioned in [Section 12.6](#).

Standard Summary Statistics for Continuous and Discrete Variables.

Summaries will be tabulated either per treatment arm or per treatment sequence, and overall (when deemed appropriate), unless otherwise specified.

Unless otherwise noted, **categorical variables** will be summarized using non-missing counts and percentages. Percentage will be using the number of patients (or the number of patients at risk) in the treatment arm/treatment sequence and as appropriate in the analyzed categories as denominator. Percentages will be rounded to one decimal place, except 100% will be displayed without any decimal places and percentages will not be displayed for zero counts.

Odd ratios (ORs) will be provided as appropriate. Odd ratios will be presented with 2 decimal places

Continuous data will be summarized using the number of non-missing observations (n), mean, standard deviation (SD), median, first quartile (Q1), third quartile (Q3), minimum (Min), and maximum (Max). Minimum and maximum, will be rounded to the precision of the original value. Mean, median, Q1 and Q3 will be rounded to 1 decimal place greater than the precision of the original value. The SD will be rounded to 2 decimal places greater than the precision of the original value. Confidence intervals (CIs), LS means, standard error (SE), geometric mean, geometric SD and coefficient of variation (CV) (%) will be provided as appropriate. Confidence intervals, LS means and geometric mean will be presented with the same precision as the mean value whereas SE and geometric SD will be presented with the same precision as SD and the CV (%) will be presented with 1 decimal place.

Inferential Statistics

P-values will be rounded to 4 decimal places. P-values less than 0.0001 will be presented as “<0.0001” and p-values greater than 0.9999 will be presented as “>0.9999.”

Statistical hypothesis testing will be 2-tailed and carried out at the 5% level of significance. Testing will be performed on the primary endpoint and secondary endpoint as appropriate.

To control for Type 1 error at a 2-sided alpha of 0.05, the primary endpoint and key secondary endpoint will be tested hierarchically, starting with the primary endpoint and followed by the secondary endpoint. No additional adjustments for multiplicity will be made for the other secondary endpoints and for exploratory endpoints although nominal p-values will be presented.

Individual Data Listings

All the listings will be displayed sorted by treatment sequence, patient identifier and date of assessment. They will present age, sex, race and country.

For those listings presenting on-treatment assessment post randomization, treatment arm along with the treatment period will also be displayed. A flag informing whether or not the data are impacted by COVID-19 may also be added.

12.1 Patient Disposition

The number and percentage of patients screened, re-screened, randomized and not randomized along with reason of screen failure will be presented using the Screening Analysis Set.

The number of patients randomized, randomized and treated, randomized and not treated, and the number of patients in each analysis set will be summarized per treatment sequence for the Randomized Analysis set.

The number and percentage of patients will also be summarized for the following patient disposition categories:

1. Completed study drug treatment per protocol
2. Discontinued study drug early and the reason for discontinuation
3. Completed the study including follow-up period
4. Discontinued from the study early and the reason for discontinuation

The table will be presented by treatment sequence, per period and overall using the Randomized Analysis Set and will be repeated for the different subgroups presented in [Table 12.1-1](#).

Table 12.1-1 Subgroups Applied to Patient Disposition

Group Variables	Subgroup	Comments
Sex	Male Female	
Age group	
 • ≤ 18 years • > 18 and ≤ 45 • ≥ 46 to ≤ 65 • > 65 	According to patient 's distribution within age, age group may be differently defined Detailed derivation is given in Section 10.10
Race	White Black or African American Asian American India or Alaska Native Native Hawaiian or Other Pacific Islander Other	According to patient's distribution within race some races may be grouped together
Prior cannabis use	Yes No	

Number of current antispasticity medication	0	
	1	
	2	
	≥ 3	

A cumulative incidence plot of permanent IMP discontinuation due to any reason will be provided by treatment sequence on the Safety Analysis Set. The Time to treatment discontinuation (in days) is defined as the number of days from 1st IMP intake until permanent treatment discontinuation (as detailed in [Section 10.6](#)). Patients who will not permanently withdraw from study drug will be censored to the earliest of last contact date and their date of completion of Period 2, whereas patients lost to follow-up will be censored at their last contact date.

A cumulative incidence plot of study discontinuation due to any reason will be provided by treatment sequence on the Randomized Analysis Set. The Time to study discontinuation (in days) is defined as the number of days from randomization until study discontinuation (as detailed in [Section 10.6](#)). Patients who will not permanently withdrawn from study drug, or lost to follow-up will be censored at their last contact date.

Each cumulative incidence plot will only be provided if more than 5 patients are presenting an event in each treatment sequence (i.e., premature end of treatment, premature study discontinuation).

A tabulation based on the Randomized Analysis Set of the number and percentage of patients randomized at country and center will be presented per randomization sequence and overall.

All patient's disposition data will be listed by treatment sequences.

12.2 Demographic and Baseline Characteristics

For all demographic and baseline characteristics assessments presented below the baseline is defined as the last available assessment collected before the first administration of study drug. Further details are given in [Section 10.2](#).

Demographic and baseline characteristics will be summarized by treatment sequence and overall using appropriate summary statistics as described in [Section 12.0](#) in the FAS and the Randomized Analysis Set if different from FAS.

If deemed appropriate (i.e., more than 20 % of the randomized patients experiencing at least one major protocol deviation, as defined in Appendix 1), demographic and selected baseline characteristics will also be summarized using the PP Analysis Set, and may also be summarized on the Study Completer Analysis Set.

All summaries for continuous parameters will be based on non-missing observation. For categorical variables, the percentage will be based on the total number of patients, within the studied dataset, overall and per treatment sequence (i.e., each denominator includes the number of patients with missing/unknown value for this parameter).

Demographic, baseline characteristics, and disease history data will also be listed with a flag identifying those belonging to the FAS, the PP Analysis Set, the Study Completer Analysis Set, and the Safety Analysis Set.

All baseline safety and efficacy parameters (apart those presented below) are presented along with summary statistics in the safety and the efficacy sections, respectively ([Section 12.7](#) and [Section 12.5](#)).

12.2.1 Demographics Characteristics

As defined in [Section 10.10](#), the following demographic and baseline characteristics will be summarized:

- Age (years),
- Age groups (≤ 18 , > 18 to ≤ 45 , ≥ 46 to ≤ 65 , > 65 years old),
- Sex (Male, Female),

- Race (White, Black or African American, Asian, American India or Alaska Native, Native Hawaiian or Other Pacific Islander, other) (per legal data protection law),
- Country (Poland, Czech Republic),

12.2.2 Baseline Physical Examination

As defined in [Section 10.11](#). the following baseline physical examination will be summarized.

- Baseline height (cm),
- Baseline weight (kg),
- Baseline BMI (kg/m²),
- Baseline BMI category (< 18.5 as underweight; ≥ 18.5 and < 25.0 as normal or Healthy Weight; ≥ 25.0 and < 30.0 as overweight; ≥ 30 as obese),

12.2.3 Baseline Vital Signs

The following baseline vital signs including postural drop assessment will be summarized.

- Baseline Supine Systolic blood pressure (SBP) (mmHg),
- Baseline Orthostatic SBP (mmHg)
Orthostatic SBP being defined as supine SBP- Standing SBP,
- Baseline Orthostatic SBP ≥ - 20 mm Hg,
- Baseline Supine Diastolic blood pressure (DBP) (mmHg),
- Baseline Orthostatic DBP (mmHg)
Orthostatic DBP being defined as supine DBP- Standing DBP,
- Baseline Orthostatic DBP ≥ - 10 mm Hg,
- Baseline Supine Heart Rate (HR) (Beats/min),
- Baseline Orthostatic HR (Beats/min)
Orthostatic HR being defined as supine HR- Standing HR,
- Proportion of patients who meet criteria for orthostatic hypotension.
defined as either drop in SBP of 20 mmHg or greater or drop in DBP of 10 mmHg or greater.

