6.2 Exclusion Criteria

The patient may not enter the trial if ANY of the following apply:

- 6.2.1 Has taken nabiximols, cannabis, or a cannabis-derived product for medicinal or recreational purposes in the 30 days prior to Visit 1 and unable to abstain for the duration of the study.
- 6.2.2 Did not tolerate or did not respond adequately to treatment with nabiximols or another cannabis-based medication if exposed at any time before the 30-day period prior to Visit 1.
- 6.2.3 Any concomitant disease or disorder that has spasticity-like symptoms or that may influence the patient's level of spasticity.
- 6.2.4 Medical history suggests that relapse/remission is likely to occur during the trial, which, in the opinion of the investigator, is expected to influence the patient's spasticity.
- 6.2.5 Has had a relapse of MS within the 60 days prior to Visit 1.
- 6.2.6 Currently using botulinum toxin injection for the relief of spasticity (within 6 months of Visit 1) and is unwilling to abstain for the duration of the trial.
- 6.2.7 Currently taking antipsychotic medication.

- 6.2.8 Currently taking benzodiazepines unless doses and dosing regimen have been stable for at least 30 days prior to Visit 1.
- 6.2.9 Clinically suspected to have a contracture in one of the muscle groups of the lower limbs, preventing assessment with the MAS.
- 6.2.10 Has any known or suspected hypersensitivity to cannabinoids or any of the excipients of the IMP.
- 6.2.11 Has experienced myocardial infarction or clinically significant cardiac dysfunction within the last 12 months prior to Visit 1 or has a cardiac disorder that, in the opinion of the investigator, would put the patient at risk of a clinically significant arrhythmia or myocardial infarction.
- 6.2.12 Has a diastolic blood pressure of < 50 mmHg or > 105 mmHg or systolic blood pressure < 90 mmHg or > 150 mmHg (when measured in a sitting position at rest for 5 minutes) or a postural drop in the systolic blood pressure of > 20 mmHg at Visit 1 or Visit 2. All measurements will be performed singly and can be repeated once, if any are outside the reference range but not considered clinically significant.
- 6.2.13 Has clinically significant impaired renal function at Visit 1, as evidenced by an estimated creatinine clearance lower than 50 mL/min. All measurements will be performed singly and can be repeated once, if any are outside the reference range but not considered clinically significant.

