9.2.10 Vital Signs

As part of the screening procedures at Visit 1, vital signs (systolic and diastolic blood pressure and pulse rate) will first be measured after the patient assumed a supine position for 5 minutes. Vital signs will then be measured within 2 minutes of assuming a standing position in ambulatory patients only. At all subsequent time points, vital sign

measurements will be completed in a sitting position at rest for 5 minutes. Blood pressure should be recorded using the same arm throughout the trial, where possible.

Additional vital signs measurements may be taken during the trial if clinically indicated.

9.2.11 12-Lead Electrocardiogram

A 12-lead ECG will be performed after 5 minutes in a supine position. A physician must review the ECG (annotated, signed, and dated) and any abnormal findings considered to indicate significant medical history or AEs must be recorded appropriately on the eCRF. Additional ECG measurements can be taken at any time during the trial, if clinically indicated.

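### SAP 12.2.3 defines a postural fall as positive but sets its two category rows at minus 20 and minus 10 mmHg, so they count every measured patient except those with a large rise

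*SAP*

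**What the plan says.** SAP 12.2.3 introduces the table with "The following baseline vital signs including postural drop assessment will be summarized". It fixes the direction of both differences: "Orthostatic SBP being defined as supine SBP- Standing SBP" and "Orthostatic DBP being defined as supine DBP- Standing DBP". The category rows are "Baseline Orthostatic SBP ≥ - 20 mm Hg" and "Baseline Orthostatic DBP ≥ - 10 mm Hg". The last bullet gives the proportion with orthostatic hypotension, "defined as either drop in SBP of 20 mmHg or greater or drop in DBP of 10 mmHg or greater".

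Two other places bear on this. Protocol 9.2.10 takes supine readings at Visit 1, followed by "Vital signs will then be measured within 2 minutes of assuming a standing position in ambulatory patients only"; all later vital signs are taken sitting. Protocol exclusion 6.2.12 rules out "a postural drop in the systolic blood pressure of > 20 mmHg at Visit 1 or Visit 2".

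**The concern.** The definition and the category limit do not fit together. If a fall is positive, a limit of minus 20 with a greater-or-equal sign does not pick out falls. It picks out everyone who does not show a marked rise. The diastolic row repeats the pattern, so this does not look like a single stray character.

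At stake is the coherence of one baseline table. A programmer following the text would produce two rows showing most measured patients at the postural threshold, next to a hypotension row that shows few. The SAP plans no other summary of supine-to-standing change: SAP 12.7.4 describes sitting pressures.

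**Working it through.** The plan states no figure to reproduce, so the check applies its definition to readings and then gauges the size under stated assumptions.

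**Inputs.** Definition D = supine - standing, systolic limit D ≥ -20, diastolic limit D ≥ -10, and the hypotension definition of a drop of 20/10 or greater, all from SAP 12.2.3.

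**Step 1: systolic examples.**

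| Supine / standing | D | Written row (D ≥ -20) | Drop of 20 or more (D ≥ 20) |
|---|---|---|---|
| 130 / 105 | +25 | counted | yes |
| 130 / 110 | +20 | counted | yes |
| 130 / 125 | +5 | counted | no |
| 130 / 130 | 0 | counted | no |
| 130 / 150 | -20 | counted | no |
| 130 / 151 | -21 | not counted | no |

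The first reading to fail the written rule is a rise of 21 mmHg. For diastolic pressure, 80/90 gives -10 and is counted; 80/91 gives -11 and is not.

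**Step 2: the opposite convention.** With standing - supine, a drop of 20 or more is ≤ -20. The written ≥ -20 would then select drops of 20 mmHg or less. That does not give the meaning of the last bullet either.

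**Step 3: internal consistency.** The hypotension row is an either/or of a systolic and a diastolic drop, so its count cannot be below that of either component. A patient with 130/130 systolic and 80/80 diastolic has D = 0 on both, is counted in both category rows, and is not hypotensive. The components will therefore exceed the composite unless virtually every measured patient has true orthostatic hypotension.

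**Step 4: size, under assumption.** The documents give no distribution, so take D as normal with mean m and SD s. The written systolic row has share 1 - Φ((-20 - m)/s); the intended row has share 1 - Φ((20 - m)/s).

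- m = 0, s = 10: 1 - Φ(-2) = 97.7% written; 1 - Φ(2) = 2.3% intended.
- m = 5, s = 10: 1 - Φ(-2.5) = 99.4% written; 1 - Φ(1.5) = 6.7% intended.
- Over m from -5 to +10 and s from 8 to 15: 84% to 100% written; 0.1% to 25% intended.
- Among patients with a drop of 20 mmHg or less, readings to 1 mmHg: 84% to 100% written; about 0% to 3% intended, since only a drop of exactly 20 qualifies.
- Diastolic, m from -5 to +5 and s from 5 to 10, limits -10 and +10: 69% to 100% written; 0.1% to 31% intended.

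**The case against.** The slip need not lie in the sign. It could be in the direction of the definition or in the inequality. Read as standing minus supine, the systolic row would select drops of 20 mmHg or less, which is exactly the group that 6.2.12 permits. This stands to the extent that the error is a mismatch between definition and limit, and the text alone does not prove which was mistyped. But 6.2.12 sets no postural limit for diastolic pressure, so that reading leaves the diastolic row unexplained. The last bullet gives the same 20/10 cut-offs as a drop or greater, which makes that the likelier intent.

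A reader might also infer that this table is the check on 6.2.12 and that, as written, it would show almost the whole trial population breaching the exclusion. The documents do not support that:

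- SAP 12.2.3 does not cite the exclusion. Eligibility deviations are handled as important protocol deviations under SAP 12.4 and Appendix 1.
- The exclusion covers Visit 1 or Visit 2, while standing readings are specified only at Visit 1 and only in ambulatory patients.
- SAP 12.2 puts patients with missing values in the denominator of categorical percentages. Non-ambulatory patients have no planned standing reading, so the printed percentage could be well below the share among those measured. Their number is not given.

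Finally, the consequence is modest. The continuous differences are defined consistently, the hypotension row is worded correctly, and a row near 100% beside it would be noticed. All of that stands.

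**Conclusion.** The two category rows are wrong as written. That they count every measured patient except those with a rise above 20 (systolic) or 10 (diastolic) mmHg follows exactly from the SAP's own definition and needs no assumption. The percentages do rest on assumed normal distributions and apply only to patients with a standing reading.

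This is a minor correction. It touches two descriptive baseline rows and leaves eligibility decisions, the efficacy analyses, the continuous postural differences and the orthostatic-hypotension row as they are.

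**What to change.** Keep the supine-minus-standing definition and change the two categories to orthostatic SBP ≥ 20 mmHg and orthostatic DBP ≥ 10 mmHg, which are the cut-offs in the section's own last bullet. State that percentages in these rows are among patients with a standing reading (Visit 1, ambulatory patients), as an exception to the general denominator rule in SAP 12.2, and print that number. Using the same denominator for the hypotension row would keep the three rows comparable.

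A further count of systolic drops above 20 mmHg is optional. It would separate a drop of exactly 20 mmHg, which 6.2.12 allows, from larger ones, but could check that exclusion at Visit 1 only.

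The cost is two corrected limits and a denominator note in the SAP, with a small programming change. The readings are already planned.
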